3.5.5 Measures and Procedures

For this survey work, interviewers will use Android tablets with specialized software for computer interviews (Survey Solutions software).

In the primary (#1) and relapse (#3) cohorts, children's anthropometric measures will be recorded during monthly home visits, and several modules of questions will be

administered to provide essential insight into relevant parental and household practices. For the treatment cohort, each nutritional unit (26) and each FARNE (about 19) will be visited by an enumerator twice a month. The enumerator will be responsible for monitoring data quality and copying data from the registers to electronic forms.

Questionnaires

- **Village/CHW/care group questionnaire**: A module of questions will be administered to the village representative at the beginning of the study. Questions about the village's infrastructure and organization and past and current health and nutrition interventions will be asked. In addition, specific questions will be asked to the community health worker and a representative of the existing care group volunteers to understand their roles, activities, motivations and knowledge of nutrition and health at the beginning of the project.
- **Health center questionnaire**: A module of questions will be administered to a manager of each health center (26) to draw up a profile of the organization of care and available inputs.
- **At the household level**: Questions on household composition, socio-economic status, household expenditures, household food security, livestock/land/asset holdings, and concession construction materials will be administered. There will be a module of questions on food hygiene, hygiene and sanitation practices. Household participation in social or NGO/government-related programs will also be assessed.
- **At the level of mothers/caregivers and children**: Questions on the level of education of the mother and father, primary occupation, decision-making power, stress, postpartum depression, and health and nutrition of the eligible child will be administered. Specific questions on nutritional, water, sanitation, hygiene knowledge and practices, and uvula removal practice will be asked to the mother/guardian in charge of the child's care. Other modules will include the use of health care services and contact times with different platforms involved in the prevention, screening, or treatment of wasting. The child's age will be obtained from a birth certificate or using a local events calendar in the event that objective proof of the date of birth cannot be presented.

Anthropometry

Anthropometric measurements will be taken during the initial and final surveys and during the monthly longitudinal follow-up visits. The child's weight will be taken using an electronic scale to the nearest 100g. The length will be measured with a measuring rod to the nearest 1 mm. The Mid-Upper Arm Circumference (MUAC) will be measured using a non-stretch tape with 0.1 cm accuracy. All measurements will be taken in

duplicate by an anthropometer and an assistant. All measurements will be standardized prior to the study. Standardization exercises using repeated measurements on 10 children aged 6-15 months will be repeated every two months. From these standardization sessions, inter- and intra-measurement variations will be documented. The weight-for-height and height-for-age z-scores will be calculated using the WHO 2006 growth standards.

The MUAC, weight and height of the mother will also be measured using a non-stretch tape, a scale, and a tape measure, respectively.

Morbidity and Mortality

During longitudinal follow-up, the assessment team investigators will conduct monthly home visits to provide a daily reminder of child morbidity (acute respiratory infections, diarrhea, fever, and malaria) over the previous 3 days. A diarrheal episode is defined as at least three loose stools in the last 24 hours, or stools with blood. Fever will be measured by a thermometer and the history of fever in the previous days will also be asked. The presence of an acute respiratory infection (ARI) in the previous week will be assessed by recalling the specific symptoms associated with ARI (cough, difficulty breathing, rapid breathing, runny nose). The presence of malaria parasites will be checked for the presence of malaria parasites with a rapid diagnostic test for malaria by capillary finger or heel swab, if body temperature is above 37.5 °C or if the mother reports a fever episode in the child within the last 72 hours.

Hemoglobin measurement on capillary blood

The hemoglobin concentration will be measured at the beginning and end of the program. For this purpose, a drop of capillary blood will be taken from the child's finger. The hemoglobin concentration will be measured by spectrophotometry using a HemoCue 301 (HemoCue Ltd, Dronfield, UK).

Anemia in children and severe anemia are defined by hemoglobin concentrations of less than 11 g.dL⁻¹ and less than 7 g.dL⁻¹ respectively.

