When community workers screen a child for acute malnutrition, the child is: i) either diagnosed as negative (code green, MUAC ≥ 125 mm); ii) or diagnosed as MAM positive ($115\text{mm} \leq \text{MUAC} < 125\text{mm}$, code yellow); iii) or diagnosed as SAM positive (MUAC $< 115\text{mm}$ or bilateral edema, code red). In the case of SAM, the mother-child couple is referred to the health center for confirmation of the diagnosis based on the MUAC and initiation of treatment. If the diagnosis is confirmed, the child is examined to verify the presence or absence of medical complications. Following the COVID19 pandemic, only the MUAC criterion is currently used to screen children.

In the absence of signs of complication, the MAM child is admitted to an outpatient program (UNS or FARNE) with a scheduled follow-up every two weeks. The duration was extended following the COVID19 pandemic; follow-up is currently monthly. The mother receives a ration of food supplements to be given to the child every day (RUSF or CSB++). In the absence of complications, and after a successful appetite test, the SAM child is included in an outpatient treatment program (UNA) with follow-up scheduled every week. The duration was extended following the COVID19 pandemic; follow-up is currently every two weeks. The mother receives a ration of food supplements (RUSF) to be given to the child every day. Complicated cases of SAM or MAM or cases with edema are referred for inpatient treatment at the hospital which has a pediatric ward (UNT ward).

Children are discharged from these treatment programs if they reach a weight-for-height->-2 z-scores and a MUAC ≥ 125 mm and the absence of bilateral edema for two consecutive visits.

c) Psycho-cognitive stimulation program at UNA/UNT

During the rehabilitation of children under treatment at UNA/UNT, their psycho-cognitive stimulation should begin, and continue after discharge, to reduce the risk of mental and physical sequels. Psychosocial stimulation should be done by the doctor and nurses. The social worker is in charge of organizing the sessions.

This program includes activities such as :

- Organizing sessions to teach mothers how to make toys themselves with cheap and salvageable materials;
- Organizing training sessions to teach mothers the importance of games and discovery in providing the psycho-cognitive and physical stimulation the child needs (this is an integral part of the treatment);

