3.3 Target population and study population

Research will be limited to the age group most at risk of wasting. Thus, for this research, the target population is all [6-23] months old children, whether healthy, wasted, or in remission of wasting, living in one of the 100 most populated villages of the Health District of Mongo (representing 8 out of 10 children in the Health District).

The study area includes 100 villages or groups of villages in the health district of Mongo located in the province of Guéra in south-central Chad.

The study populations will be composed of :

- 1- Children recruited at 6 months of age in the 100 most populated villages and followed throughout the study. Children will be enrolled every month during the first 7 months of the study. Including the month of inclusion, children will therefore be followed for 9 months (for children enrolled at the beginning of the study) and for a minimum of 3 months (for children enrolled during the 7th month).

- 2- [6-23] months old children living in the 100 most populated villages, discharged from treatment in the nutritional units and FARNE and followed for a period of 6 months.
- 3- [6-23] months old children living in the 100 most populated villages, enrolled in a wasting treatment program in the nutritional units (UNA, UNS) and the FARNE, and followed up until the end of the program.

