Month of inclusion 5 (n = 250)						n = 1250			
Month of inclusion 6 (n = 250)							n = 1500		
Month of inclusion 7 (n = 250)							n = 1750	n = 1750	n = 1750
Relapse Prevention Cohort									
Month of inclusion 2 (n = 350)					n = 350				
Month of inclusion 3 (n = 350)					n = 700	n = 700	n = 700	n = 700	n = 700
Total number of children in the two cohorts									
	250	850	1450	1700	1950	2200	2450	2450	2100

The treatment cohort (#2) will include all records of children (aged [6-23] months) living in the 100 villages in the study area and enrolled between April 2021 and December 2021 in a treatment program by the national PCIMA program (UNA, UNS, FARNE, UNT). Treatment data are collected by the health centers as part of their routine.

Each nutritional unit and FARNE will be visited by an enumerator twice a month.

The enumerator will be responsible for monitoring data quality and copying data from the registers to electronic forms.

The copied data will not personally identify the children, except for the children followed in cohorts 1 and 3 whose parents will give their consent as part of the informed consent process to link the treatment data to their cohort data. For other registry data for children outside of cohorts 1 and 3, there is no provision for seeking parental consent as we will treat these data as secondary data. No follow-up visits will be made by the interviewers, so they will not attempt to locate the children. **Thus, the data copied will not include names, phone numbers, or dates of birth.** However, it will include other variables such as anthropometric measures and inputs given and services received, as well as sex, age group, and village code, solely for the purpose of accounting for these primary adjustment factors and the cluster effect when analyzing the data.

The criteria for inclusion in the treatment cohort are :

- The child is included in a national treatment program.
- The child is between 6 and 23 months of age at inclusion
- Child lives in one of the 100 villages in the study area

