3.5.4 Study Results

For this study, wasting is defined by WHZ <-2 (relative to the WHO reference of 2006) or MUAC <125 mm or bilateral edema. Moderate Acute Malnutrition (MAM) is defined by -3≤ WHZ <-2 (relative to WHO reference of 2006) or 115mm≤MUAC <125 mm. Severe Acute Malnutrition is defined by WHZ <-3 (relative to WHO 2006 reference) or MUAC <115 mm or bilateral edema.

The **main results of the study** are:

1. Longitudinal prevalence of wasting among children enrolled at 6 months of age followed monthly until the end of the study (Cohort 1). This indicator is defined for each child as the number of visits during which wasting is observed divided by the total number of monthly visits made (by interviewers).
2. The recovery rate in children enrolled at [6-23] months of age for up to 3 months of treatment in a UNS, UNA or FARNE and followed through to discharge (Cohort 2). This indicator is defined as the number of discharges considered cured according to national program criteria (WHZ>-2 and MUAC>=125mm and absence of bilateral edema for two consecutive visits, within 12 weeks of enrollment in the program) divided by the total number of discharges recorded.

3. The incidence of wasting in children enrolled at [6-23] months of age at discharge and followed for 6 months (Cohort 3). This indicator is defined as the number of new cases of wasting recorded during monthly visits.

Secondary outcomes of the study include:

For Cohorts 1 and 3 :

- The longitudinal prevalence of :
 - o MAM, defined by the number of MAM diagnoses divided by the total number of monthly visits made
 - o SAM, defined by the number of SAM diagnoses divided by the total number of monthly visits made
- The impact of :
 - o Wasting, defined by the number of new cases of wasting recorded during monthly visits.
 - o MAM, defined by the number of new MAM cases recorded during monthly visits
 - o SAM, defined by the number of new SAM cases recorded during monthly visits
- The prevalence of anemia defined as the proportion of children with a hemoglobin level below 11g/dl at the end of the study.
- Mean hemoglobin concentration at the end of the study
- Prevalence of stunting defined as the proportion of children with HAZ <-2 (relative to the 2006 WHO reference) at the end of the study.
- The average z-scores HAZ at the end of the study

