In the intervention villages, all households with a pregnant woman and/or a child below 2 years of age will be eligible to be enrolled for follow-up by a community care group member and will receive the intervention components described in Table 1 depending on the child age and nutritional status.

Considering the short time frame to conduct the study, the research is limited to the age group most at risk of wasting. Thus, the target population comprises all [6-23] months old children of the study area, whether healthy, wasted, or recovered from wasting.

We will follow an open cohort (**main cohort**) of children aged 6 to 6.9 months, included for a period of 7 months and followed up monthly until the end of the study; and will assess the overall impact of the intervention on the longitudinal prevalence of wasting, as well as on secondary outcomes (described below in section 3.4).

In addition, we will follow two other cohorts to further study the impact of the intervention in the subgroup of children enrolled for treatment, and in the subgroup of recovered children.

- For the **treatment cohort**, we will use health system records to enroll all children aged 6-23 mo living in the 100 villages of study area and admitted for wasting treatment at a health center or a community site in the Mongo District during the study period. We will follow them from program admission to program exit, using the registers data, and will study the impact on the recovery rate and other secondary outcomes.
- For the **relapse prevention cohort**, we will follow for 6 months a cohort of children aged 6-23 mo who have been treated and have recovered from wasting and will assess the impact of the intervention on the incidence of relapse, as well as on secondary outcomes.

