 - Minimum meal frequency for children, defined as the proportion of children who had eaten the day before the survey: 2 meals for breastfed children 6-8 months, 3 meals for breastfed children 9-23 months, or 4 meals for non-breastfed children 6-23 months.
 - Minimum acceptable diet, defined as the proportion of children with both minimal dietary diversity and minimal meal frequency on the day before the survey.
 - Consumption of iron-rich or iron-fortified foods in children.
- Practices related to water, hygiene and sanitation, as per Standard USAID indicators related to drinking water source, treatment, storage; hand washing; and sanitation
- Vaccination coverage, defined as the proportion of children with complete vaccination for their age.

For Cohort 2⁵:

- Nutritional status (measured by MUAC) at admission in treatment unit.
- The duration of treatment defined as the number of days spent on treatment (between admission and discharge).
- Treatment adherence defined as the proportion of cases enrolled for treatment who received timely treatment from dedicated services until recovery.
- The treatment outcome (drop-out, death, transfer, non-response rates).
- longitudinal prevalence of childhood morbidity defined by the number of days for which signs of these morbidities were reported divided by the total number of days observed/reported in the recall periods.

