Exclusion criteria	Congenital malformations that make anthropometric measurements impossible. Mother intends to leave the study area by December 2021.	None.	Congenital malformations that make anthropometric measurements impossible. Mother intends to leave the study area by December 2021.
Sample size	1,750 children	Exhaustive inclusion	700 children
Intended duration of inclusion	7 months	9 months	2 months
Follow-up frequency	Monthly	Bi-monthly visit by enumerators to health center treatment units, and monthly visits to community treatment units.	Monthly
Intended study duration	enrolled children will be followed until the end of the study, with a total study duration of 9 months	from program admission to program exit, with a total study duration of 9 months.	Follow-up of all children for 6 months, with a total study duration of 8 months.
Changes to the protocol	November 2021: Study duration was increased by a month and exits were split evenly across the 2 last months of the study, based on enrollment order.	November 2021: Study duration was increased by a month.	November 2021: To meet the sample size, we extended the inclusion duration to 7 months January 2022: To meet the sample size, we extended the inclusion duration to 9 months, and we released the limitation on the maximum number of children per village. We also extended the total study to 12 months, and enrolled children will be followed-up either for 6 months, or until the end of the study, whatever comes first.

4 Data management

The management of all research data will follow IFPRI's institutional research data management protocol, overseen by the IFPRI Data Governance Committee, as well as UNICEF data governance standards. All received data will be carefully anonymized and de-identified so that the privacy of participants and research subjects is fully protected. Personally Identifiable Information data (PII; names, telephone

numbers, GPS coordinates, date of birth) will be stripped from the research data when receiving the data on the server. During data collection, PII data will be stored in a separate secured server folder accessible only to the Principal Investigators. PII data will only be used to identify a household to conduct additional verification of previously collected data. When data collection and data validation have been completed, PII data will be destroyed.

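### Cohort 2 does not settle whether inpatient (UNT) records belong to it, so outcomes after referral have no specified capture and transfers can be misclassified in the recovery rate

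*Protocol*

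**What the plan says.** **UNT in.** Protocol 3.5.3 defines cohort 2 as all records of eligible children enrolled "in a treatment program by the national PCIMA program (UNA, UNS, FARNE, UNT").

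**UNT not mentioned.** Protocol 3.3 describes the same cohort as children "enrolled in a wasting treatment program in the nutritional units (UNA, UNS) and the FARNE". Protocol 3.5.1 names UNS and UNA, at the health center and the FARNE site. Protocol 3.5.4 defines the primary outcome "for up to 3 months of treatment in a UNS, UNA or FARNE and followed through to discharge". The visit plan in Protocol 3.5.5 is: "For the treatment cohort, each nutritional unit (26) and each FARNE (about 19) will be visited by an enumerator twice a month". The SAP design text (3.2) takes children "admitted for wasting treatment at a health center or a community site in the Mongo District during the study period", and SAP Table 2 (3.6) schedules "Bi-monthly visit by enumerators to health center treatment units, and monthly visits to community treatment units".

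**Silent.** The selection row of SAP Table 2 admits any child in the national CMAM program and has each treatment unit visited. It neither names nor excludes the UNT.

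**Referral and outcomes.** Protocol 3.1.2 places the UNT in the district hospital and states: "Complicated cases of SAM or MAM or cases with edema are referred for inpatient treatment at the hospital". SAP 3.4.2 reports "The treatment outcome (drop-out, death, transfer, non-response rates") for cohort 2. SAP 3.4.1 divides recoveries by all recorded exits. SAP 5.2 recodes any other exit type to recovered when exit MUAC is 125 mm or more.

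**The concern.** If enumerators follow the visit plan, a child who starts as an outpatient and is then referred to hospital leaves cohort 2 as a transfer, and nothing says that the inpatient result will be read. A child sent straight to hospital may not appear in cohort 2 at all. These are the complicated and edema cases.

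Two results are affected. The first is death. The outcome lists contain no other death outcome, and Protocol 3.5.5 has a morbidity and mortality heading but defines no mortality measure under it. The second is the cohort 2 primary outcome. A transfer stays in the recovery denominator as a non-recovery, unless the recode turns it into a recovery. The intervention could change the transfer share in either direction: earlier detection may reduce complicated cases, while closer follow-up may raise referrals. Part of the recovery contrast would then come from transfers rather than from treatment results.

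**Working it through.** **1. Is the UNT among the sites visited?** Protocol 3.1.1 and 3.5.5 both give 26 health centers, and the visit plan gives 26 nutritional units. The UNT is in the hospital, so a count of 26 leaves no room for it. This is an inference, since a UNT is by name also a nutritional unit. SAP Table 2 supports it by scheduling only health center and community units.

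**2. The plan's own figure.** Inputs from SAP 3.5.2: 100 clusters (50 per arm), 78 cases each, recovery 85%, ICC 0.05, power 80%, type I error 5% (two-sided, SAP 6.1).
- Cases: 2 × 3,928 = 7,856, or 78.6 per cluster.
- Design effect: 1 + (78 − 1) × 0.05 = 4.85.
- Effective n per arm: 50 × 78 / 4.85 = 804.
- Detectable difference: 4.6 points upward (85% to 89.6%) or 5.3 points downward (85% to 79.7%).

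This reproduces the stated ~5 points. Losing an assumed 1% to 10% of cases to the UNT moves it only to 4.65-4.69 points upward or 5.33-5.39 downward, so power is not the issue.

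**3. Effect of transfers on recovery.** Let *s* be the transfer share of exits and *r* the recovery probability that transferred children would have had if followed through. Neither is in the documents. Assume 85% recovery among the others.
- Transfers as non-recovery: measured rate = 0.85 × (1 − s). For s = 1%, 3%, 5%, 10% this is 84.2%, 82.5%, 80.8%, 76.5%.
- Error against full follow-up: −r × s. If the shares differ between arms by *d*, the contrast shifts by r × d.
- At r = 85%: d = 1, 2, 5 points gives 0.85, 1.7, 4.3 points. At r = 50%: 0.5, 1.0, 2.5 points.
- Equal shares lower both arms and only scale the contrast by (1 − s); at s = 5%, a 5-point difference becomes 4.75.
- If instead a transfer has exit MUAC of 125 mm or more and is recoded, the error is +(1 − r) per transfer, in the opposite direction.

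The redefined outcome in SAP 3.4.1 no longer uses edema. Read literally, an edema case transferred with MUAC of 125 mm or more is a recovery, whatever happens in hospital. The recode likewise does not exempt a death.

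**4. Deaths.** Protocol 3.1.1 gives a death rate of around 0.5%, from admissions to outpatient or therapeutic units and discussed as severe-wasting services.
- SAM cases only: 0.005 × 3,928 = 19.6.
- All cases: 0.005 × 7,856 = 39.3.
- If 25% to 75% of deaths occur in the UNT (assumed): from 0.25 × 19.6 = 4.9 to 0.75 × 39.3 = 29.5.

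**The case against.** The strongest reply is that the UNT in Protocol 3.5.3 is a stray word. Protocol 3.3, 3.5.1 and 3.5.4 all describe outpatient and community treatment, so cohort 2 is coherent without the hospital. That may be the intent. It does not supply a rule for transfers, and the death outcome would still need a label showing its scope.

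A reader might infer stronger things that the documents do not support:
- *The SAP drops units that the protocol includes.* The conflict is already inside the protocol, and the selection row of SAP Table 2 does not exclude the UNT.
- *All complicated and edema cases exit as transfers and count as failures.* Those complicated at presentation may never enter an outpatient register, and the SAP 5.2 recode can make a transfer a recovery.
- *Later deaths are never counted.* Children in cohorts 1 and 3 are visited monthly and can be linked with consent (Protocol 3.5.3). For the others, capture is unspecified.
- *A 3-5% transfer share nearly uses up the detectable difference.* That compares a level shift in both arms with a between-arm contrast. Shares of 3% against 5% shift the contrast by about 1.7 points at r = 85%.

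Two further points stand. SAP 3.2 already calls cohort 2 quasi-experimental, and transfer is reported separately, so a difference between arms would be visible. Death is also a weak comparison with or without the UNT. With 3,928 per arm and clustering ignored, a fall from 0.5% to 0.15% gives z = 0.0035 / 0.00128 = 2.7, just under 80% power. That is a reduction of about 70%. None of this removes the gap in the primary outcome: SAP 6.4.3 has no sensitivity analysis for cohort 2.

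**Conclusion.** The concern holds in a limited form. The documents disagree on whether UNT records belong to cohort 2, and the operational text points to their not being read. The death rate would then describe outpatient treatment only, and could not be set beside the district's 0.5%, which appears to include inpatient units. In the recovery rate, transfers can be misclassified in either direction. Bias in the contrast comes essentially from a difference in transfer share between arms. It is about 0.85 points per 1-point difference when transfers count as non-recovered and r = 85%. That value of r is an upper assumption, since these are the sicker children. A 5-point difference in share would be needed to approach the detectable ~5 points, and no share or difference is documented. The figure of 5 to 29 deaths rests on an assumed split and on which cases the 0.5% applies to. The ~5-point sample-size figure is not in error on this point.

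**What to change.** 1. Reconcile Protocol 3.3, 3.5.1, 3.5.3, 3.5.4 and 3.5.5 with SAP 3.2 and Table 2, stating whether UNT records are in cohort 2.
2. If they are, add the hospital register to the sites copied, using the anonymous fields that Protocol 3.5.3 already allows. Report UNT admissions and deaths by village and arm as a separate count. Do not form a rate per first admission, because most children cannot be linked. If they are not, delete the UNT from Protocol 3.5.3 and label the outcome as death during outpatient treatment.
3. Exempt transfers and deaths from the SAP 5.2 recode to recovered.
4. Report the transfer share by arm, and show recovery with transfers excluded as a sensitivity analysis only, noting that this conditions on a post-randomisation event.

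**Cost.** One more register at one hospital if the UNT is kept, otherwise wording only, plus one extra analysis. The documents do not say whether that register records the village, so this must be checked first. Inpatient deaths of children without consent to linkage still cannot be tied to their outpatient record.
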